4.3.2 Angiographic Exclusion Criteria

- More than two lesions requiring treatment.
- Unprotected left main coronary artery disease. (Greater than 50% diameter stenosis)
- Coronary artery spasm of the target vessel in the absence of a significant stenosis.
- Target lesion with angiographic presence of probable or definite thrombus.
- Target lesion involves a bifurcation requiring treatment with more than one stent or pre-dilatation of a side branch > 2.0 mm in diameter.

- Non-target lesion to be treated during the index procedure meets any of the following criteria:
 - Located within a bypass graft (venous or arterial)
 - Left main location
 - Chronic total occlusion
 - Involves a bifurcation (e.g., bifurcations requiring treatment with more than 1 stent)
 - Treatment not deemed a clinical angiographic success.

4.4 Subject Withdrawal Criteria

Each enrolled subject shall remain in the study until completion of the required follow-up period, however, a subject's participation in any clinical study is voluntary and the patient has the right to withdraw at any time without penalty or loss of benefit. Conceivable reasons for discontinuation may include, but not be limited to, the following:

- Subject death
- Subject voluntary withdrawal
- Subject withdrawal by physician as clinically indicated
- Subject lost-to follow-up

The reason for subject discontinuation must be documented on the CRF and source documents. The Primary Investigators must also report all subject discontinuations to their IRB, MEC, or HREC as defined by their Institution's procedure.

5 Treatment of Subjects

A maximum of two lesions, including at least one target lesion, may be treated during the index procedure.

Non-target lesion should be treated first and deemed a clinical angiographic success by visual assessment prior to treatment of the target lesion.

The lesion identified as the Target lesion is intended to be dilated first during the index procedure with a Sapphire II PRO 1.0 or 1.25 coronary dilatation catheter.

5.1 Non-Target Lesion

- A maximum of one non-target lesion (in addition to one target lesion in a target vessel) may be treated in a non-target vessel with a commercial treatment during the index procedure and must be completed prior to treatment of target lesion.
- Treatment of non-target lesion must be deemed a clinical angiographic success as visually assessed by the physician for subjects to be eligible for enrollment into the study.
- Target and non-target lesions must be located in different coronary arteries or bypass grafts.

5.2 Target Lesion

- Lesion that is to be treated with the study device during the index procedure.
- Target lesions may be located in the same or different coronary arteries or bypass grafts.
- Target lesion composed of multiple focal lesions that can be covered with one stent will be considered as a single lesion.
- One Sapphire II PRO PTCA dilatation catheter may be used for treatment of two separate target lesions located in the same vessel. It is recommended that treatment of the distal lesion occurs prior to treatment of a more proximal lesion.
 - *Note:* A separate Sapphire II PRO PTCA dilatation catheter must be used for treatment of each target lesion if located in separate target vessels.

Table 1.0 Schedule of Procedures

	Screening and Pre-Enrollment	Postprocedure	Discharge
Enrollment and / Pre-dilatation Procedure			
Study Eligibility	X		
Informed consent	X		
Medical history	X		
Physical assessment, including vital signs	X		X
Angina class	X	X	X
12-lead ECG	X	X	
Medication review	X		X
Pregnancy test (women only)	X		
Laboratory Tests			
Serum Creatinine	X		
CBC with platelets	X		
CK Total/ CK-MB		X ^a	X ^b
Heart catheterization	X	X	
Pre-dilatation procedure		X	
Angiographic Assessment			X
Review of Adverse medical events and device-related events		X	X

a. All subjects must have CK/CK-MB drawn within 24 hours before the procedure to determine eligibility; however, if the results are not available, eligibility may be based upon troponin values.

b. For three CK-MB draws. The first draw should be performed immediately after the procedure, the second draw should be performed 6-12 hours post-procedure and the third draw should be performed 18-24 hours post-procedure. If the subject is discharged prior to 18 hours post procedure, the third CK-MB draw should be obtained at the time of discharge

5.3 Study procedures

5.3.1 Written Informed Consent

Written informed consent must be obtained prior to initiation of any study-related procedures that are performed solely for the purpose of determining eligibility to participate in the study. Once the subjects have signed the Institutional Review Board (IRB) approved study informed consent form (ICF) and research authorization forms (RA/HIPAA) and have met all general inclusion and exclusion criteria, the subjects will be considered eligible to be enrolled in the study to receive treatment with the either the 1.0 or 1.25 mm diameter Sapphire II PRO dilatation catheter. A subject is considered enrolled in the study upon insertion of the investigational device into a guide catheter. Upon enrollment, a subject identification number will be assigned to each subject in a consecutive manner within each clinical site.

5.3.2 Within 24 hours Prior to Index Procedure

The following pre-procedure data must be collected within 24 hours prior to the index procedure for all subjects:

- Current antiplatelet, anti-thrombotic and cardiac medications
- 12-lead electrocardiogram (ECG)
- Laboratory tests:
 - Cardiac enzymes: CK Total and, if CK Total is abnormal (>1x ULN), CK-MB must be performed.
 - If CK/CK-MB results are not available; eligibility may be based upon troponin values.

5.3.3 Index Procedure

The start of the index procedure is defined as the time of sheath insertion. If a previously placed sheath is used (i.e., from an earlier diagnostic procedure), index procedure start time is defined as the time of guide catheter insertion into sheath for wiring the target lesion. During cardiac catheterization, the following procedures and assessments must be completed.

- Perform angiography according to the Angiographic Core Laboratory procedure guidelines.
- Confirm angiographic eligibility criteria.
- Treat the non-target lesion, if any, prior to treatment of the target lesion as described in Section 6.1.
- If treatment of non-target lesion was successful, continue with enrolling the subject in the study.

- Pre-dilate each target lesion, if more than one, with Sapphire II PRO dilatation catheter, and perform an angiogram during inflation of the study balloon to define the point of pre-dilatation during the index procedure.

5.3.4 Completion of Index Procedure

The completion of the Index Procedure is defined as the time the guide catheter is removed, post final angiography. The following information should be collected:

- Document procedural information, including non-target lesion (if applicable), target lesion, pre-dilatation with a study balloon, stent (if applicable) and post-dilatation (if applicable) on the appropriate CRFs.
- Record cardiac medications
- Record antithrombotic and antiplatelet medications.
- If an AE should occur, Complete AE assessment and source document collection
- Record any device deficiencies that might have occurred before or during the procedure as described in Section 8.

5.3.5 Hospital Discharge/ End of Study

The following information must be collected post index procedure:

- Clinical Status assessment including Angina assessment/Ischemia classification.
- 12-lead ECG within 24 hours after the index procedure or prior to hospital discharge, whichever occurs first.
- CK-MB: CK-MB draws must be obtained within 24 hours post-procedure. The first draw should be performed immediately after the procedure, the second draw should be performed 6-12 hours post-procedure and the third draw should be performed 18-24 hours post-procedure.
- **Note:** If the subject is discharged prior to 18 hours-post procedure, the third CKMB draw must be obtained at the time of discharge (it is recommended that in these cases the third CK-MB draw occurs no earlier than 16 hours post-procedure).
- Record cardiac medications including antiplatelet and anti-thrombotic therapy
- If an AE should occur, Complete AE assessment and source document collection

6 Assessment of Safety and Efficacy

Clinical events and procedural device success will be assessed per patient.

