6.2.2 In-hospital Clinical Safety and Efficacy

The following end-points will be measured through hospital discharge:

- In-hospital Major Adverse Cardiac Events (MACE), a composite of:
 - All death (cardiac and non-cardiac)
 - Myocardial infarction (MI)
 - Target Lesion Revascularization (TLR), clinically indicated
- Individual components of the MACE composite end-point
- In-hospital Target Lesion Failure (TLF) a composite of:
 - Cardiac death
 - Target vessel MI
 - TLR, clinically indicated
- In-hospital stent thrombosis (ST) within the target vessel
- Clinically significant arrhythmias (requiring intervention)

Both MI and ST are to be determined by the Academic Research Consortium (ARC) classification criteria.⁸ MI to be classified into various types and include the 99th percentile upper reference limit (URL) decision limits for biomarkers employed.⁹

Myocardial Infarction will be defined as:

- Q-Wave MI: Development of new (i.e., not present on the subject's ECG before allocation) pathological Q-waves in 2 or more leads lasting 0.04 seconds with post-procedure CK-MB levels elevated above normal.
- Non-Q-Wave MI: Elevation of post-procedure CK-MB levels to >3.0 times ULN without new Q-waves.

For subjects undergoing bypass surgery, a peri-operative MI will be defined as follows:

- a) Total CK-MB $>5\times$ ULN.
or
- b) Presence of new pathologic Q-waves as defined above.

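### The one required post-procedure ECG has a latest time but no earliest time, so it can precede the CK-MB draws it is read with and under-count MI

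*Protocol*

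**What the plan says.** The post-procedure ECG requirement is one line in Protocol Section 5.3.5: "12-lead ECG within 24 hours after the index procedure or prior to hospital discharge, whichever occurs first". The clock starts when the index procedure ends, which Section 5.3.4 fixes as follows: "The completion of the Index Procedure is defined as the time the guide catheter is removed, post final angiography". The comparison tracing is the baseline ECG listed in Section 5.3.2 under "The following pre-procedure data must be collected within 24 hours prior to the index procedure for all subjects".

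CK-MB has a different schedule. Section 5.3.5 sets three timed draws: one immediately after the procedure, one at 6-12 h, and a last one of which it says "the third draw should be performed 18-24 hours post-procedure". A subject who leaves before 18 h has the last draw at discharge, with a recommendation that it be no earlier than 16 h.

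Section 6.2.2 says of MI, MACE and TLF: "The following end-points will be measured through hospital discharge". It calls a Q-wave MI the appearance of new "pathological Q-waves in 2 or more leads lasting 0.04 seconds with post-procedure CK-MB levels elevated above normal". The other type is "Non-Q-Wave MI: Elevation of post-procedure CK-MB levels to >3.0 times ULN without new Q-waves". The same section also says that MI is to be determined by ARC criteria and is to include 99th-percentile limits for the biomarkers, without writing those thresholds out.

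Table 4 of the SAP has a single post-PCI ECG block.

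**The concern.** The Q-wave definition has two halves, a biomarker and an ECG, and they are sampled on different clocks. The biomarker is followed for most of a day. The ECG may be recorded once, minutes after the procedure, and the schedule then asks for nothing more. No rule calls for another tracing if a later CK-MB draw comes back raised.

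For some subjects the ECG decides whether an MI is counted at all. If their only tracing was taken before the Q-waves appeared, the event drops out of the MI rate and the MACE rate. Acute safety is a stated objective (Protocol Section 3), and in a study of 60 a single event is visible in the result.

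**Working it through.** The plan states no figure on this point, so there is none to reproduce. The check compares the two schedules, enumerates the written MI rule, and then sizes one missed case.

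**Step 1. The two schedules** (Protocol Sections 5.3.4 and 5.3.5)

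| | Earliest time | Latest time | Number |
|---|---|---|---|
| ECG | none; from guide-catheter removal | 24 h, or discharge if sooner | 1 |
| CK-MB | immediate | 18-24 h, or discharge if sooner | 3 |

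A compliant ECG can therefore precede both the 6-12 h and the 18-24 h draws. Table 1.0 is not used as evidence, because its columns appear shifted in the copy available.

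**Step 2. The written MI rule** (Protocol Section 6.2.2, non-surgical subjects)

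The term above normal is read as more than 1 times ULN. That is an assumption, taken from Section 5.3.2, which uses that cut-off for total CK: "if CK Total is abnormal (>1x ULN), CK-MB must be performed".

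| Post-procedure CK-MB | No new Q-waves | New Q-waves |
|---|---|---|
| up to 1x ULN | no MI | no MI |
| above 1x, up to 3x ULN | **no MI** | **Q-wave MI** |
| above 3x ULN | non-Q-wave MI | Q-wave MI |

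Only in the middle row does the ECG change MI from no to yes. Above 3 times ULN it changes only the type. After bypass surgery the written biomarker threshold is above 5 times ULN, so the range in which Q-waves decide is wider.

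**Step 3. Direction**

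Suppose a subject has the ECG soon after catheter removal, with no new Q-waves, and CK-MB then rises to 2 times ULN at 6-12 h. If new Q-waves appear after the tracing and no further ECG is taken, the subject is placed in the left-hand cell of the middle row and not the right-hand one. Missing a Q-wave can remove an MI but cannot create one, so the error runs one way.

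**Step 4. Size of one missed case**

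With N = 60 subjects and complete data, 1/60 = 1.67 percentage points. Exact (Clopper-Pearson) 95% intervals:

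| Events | Rate | 95% interval |
|---|---|---|
| 0 of 60 | 0% | 0 to 5.96% |
| 1 of 60 | 1.67% | 0.04 to 8.94% |
| 2 of 60 | 3.33% | 0.41 to 11.53% |

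Missing the only event would move the upper limit from 8.94% to 5.96%. MACE falls by the same 1.67 points only if the subject has no other MACE component. TLF falls only if the MI is in the target vessel and no other TLF component is present.

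**Step 5. How often**

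The documents give no rate. If p is the assumed chance per subject of such a missed case, the chance of at least one in 60 is 1 − (1 − p)^60:

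| Assumed p | Chance of at least one |
|---|---|
| 0.1% | 5.8% |
| 0.5% | 26% |
| 1% | 45% |
| 2% | 70% |

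These rates are illustrations, not estimates, and the range is too wide to support any claim about the likely effect.

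**The case against.** The case against is mostly about how far the point reaches, and much of it stands.

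- **Other routes to MI.** A reader might infer that new Q-waves are the sole route to MI in the 1-3 times ULN band. That is true of the written Q-wave and non-Q-wave lines, but Section 6.2.2 also invokes ARC and 99th-percentile criteria. Their thresholds are not in the documents, so other routes cannot be ruled out. This stands and limits the claim.
- **The clause does not ask for an early tracing.** A reader might take the choice of the earlier of 24 h and discharge as pushing sites to record early. It only sets the deadline. A tracing at a few minutes is permitted, but nothing shows it is expected practice.
- **The speed of Q-wave development is not in the documents.** Section 6.2.2 uses new in the sense of absent at baseline and says nothing about hours. The point needs only that a tracing cannot show what comes after it.
- **There are other safeguards.** Section 5.3.5 requires clinical and angina assessment, the CK-MB draws and source documents for adverse events. Section 6.4 sends clinical endpoints to an independent committee. A clinically recognised later event may well have its own ECG. But the committee can judge only tracings that exist, and no rule prompts one when CK-MB alone rises. The exposed case is narrow, but not closed.
- **Limited consequence.** The primary endpoint does not use the ECG, the analysis is descriptive, and no between-site comparison is planned. A reader might infer that variable timing biases a comparison or threatens the main result; the documents support neither.

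**Conclusion.** The point holds in a limited form. The protocol lets the single required ECG precede the later CK-MB draws. Under the written Q-wave and non-Q-wave definitions, that can turn an MI with CK-MB above 1 and up to 3 times ULN into a non-event. The error can only reduce MI and MACE, by 1.7 percentage points per missed subject out of 60, and TLF under the target-vessel condition.

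This rests on three assumptions: above normal means more than 1 times ULN; the written definitions are the ones applied, and the ARC and 99th-percentile sentence does not capture the same subjects; and no unscheduled ECG is recorded. How often all this would coincide is unknown. It is a small, unquantified weakness in a secondary safety endpoint, worth correcting because correction costs almost nothing. The documents do not show that MI is in fact under-counted.

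**What to change.** In Protocol Section 5.3.5, replace the ECG line with: *12-lead ECG at the time of the third CK-MB draw (18-24 h post-procedure, or at discharge if earlier); this is the tracing used for the new Q-wave reading.* Align the ECG row of Table 1.0 with it.

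The cost is one sentence and one table row. The number of study ECGs is unchanged, the new time lies inside the existing window, and only assessment timing is affected. There are two drawbacks. A site that routinely records an ECG straight after PCI could no longer use it as the study tracing. And a subject kept beyond 24 h would still have no scheduled ECG for the rest of the stay, so the change closes the gap with the biomarker schedule but not the whole interval to discharge.

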6.1 Primary end-point

The study primary end-point shall be defined as Device Procedural Success consisting of a composite of the following parameters:

- Successful delivery, inflation, deflation and withdrawal of the study balloon
- No evidence of vessel perforation, flow limiting dissection (grade C or higher) or reduction in TIMI flow from baseline related to the study balloon
- Final TIMI flow grade of 3 at the conclusion of the PCI procedure

6.2 Secondary end-points

6.2.1 Procedure-Related

The following peri-procedural end-points of study device effectiveness will be determined:

- Successful delivery, inflation, deflation, and withdrawal of the study balloon
- Absence of vessel perforation, flow limiting dissection (grade C or higher, or reduction in TIMI flow from baseline related to the study balloon)
- Absence of balloon rupture of the study balloon
- Improvement in Minimum Lumen Diameter (MLD) following pre-dilatation with Sapphire II PRO Ø1.0 and 1.25 mm PTCA dilatation catheters (measured by QCA)
- And Lesion Success defined as successful PCI in the absence of vessel perforation, flow limiting dissection (grade C or higher, reduction in TIMI flow from baseline related to the study balloon, or clinically significant arrhythmias

6.2.2 In-hospital Clinical Safety and Efficacy

The following end-points will be measured through hospital discharge:

- In-hospital Major Adverse Cardiac Events (MACE), a composite of:
 - All death (cardiac and non-cardiac)
 - Myocardial infarction (MI)
 - Target Lesion Revascularization (TLR), clinically indicated
- Individual components of the MACE composite end-point
- In-hospital Target Lesion Failure (TLF) a composite of:
 - Cardiac death
 - Target vessel MI
 - TLR, clinically indicated
- In-hospital stent thrombosis (ST) within the target vessel
- Clinically significant arrhythmias (requiring intervention)

Both MI and ST are to be determined by the Academic Research Consortium (ARC) classification criteria.⁸ MI to be classified into various types and include the 99th percentile upper reference limit (URL) decision limits for biomarkers employed.⁹

Myocardial Infarction will be defined as:

- Q-Wave MI: Development of new (i.e., not present on the subject's ECG before allocation) pathological Q-waves in 2 or more leads lasting 0.04 seconds with post-procedure CK-MB levels elevated above normal.
- Non-Q-Wave MI: Elevation of post-procedure CK-MB levels to >3.0 times ULN without new Q-waves.

For subjects undergoing bypass surgery, a peri-operative MI will be defined as follows:

- a) Total CK-MB $>5\times$ ULN.
or
- b) Presence of new pathologic Q-waves as defined above.

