6.4 Clinical Events Adjudication

All clinical end-points are to be adjudicated by an independent clinical events committee using definitions consistent with the investigational plan. The CEC will develop a prospective CEC charter before any study data is adjudicated.

7 Adverse Events

An AE is defined as any untoward medical occurrence, unintended disease or injury, or untoward clinical signs (including abnormal laboratory findings) in subjects, users, or other persons, whether or not related to the investigational medical device.

Any pre-existing condition known to the investigator will not, in general, be reportable as an AE, unless the investigator believes that the participation of the subject in this study contributed to the progression of that condition.

When an AE has, by its nature, a prolonged course, the event will be considered a single event and not multiple events.

Death itself should not be recorded as an AE, but should only be reflected as an outcome of another specific AE. Any AE experienced by the study subjects after enrollment and up until index procedure hospital discharge must be recorded in the CRF.

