#### 5.2.2. In-hospital Clinical Safety and Efficacy

The following end-points will be measured through hospital discharge:

- In-hospital Major Adverse Cardiac Events (MACE), a composite of:

- All death (cardiac and non-cardiac)
- Myocardial infarction (MI)
- Target Lesion Revascularization (TLR), clinically indicated
- Individual components of the MACE composite end-point
- In-hospital Target Lesion Failure (TLF) a composite of:
  - Cardiac death
  - Target vessel MI
  - TLR, clinically indicated
- In-hospital stent thrombosis (ST) within the target vessel
- Clinically significant arrhythmias (requiring intervention)

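### Could the non-Q-wave MI rule in Protocol 6.2.2 count a CK-MB value that was already raised before the procedure as an in-hospital MI?

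*Protocol*

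**What the plan says.** Protocol 6.2.2 describes MI in two ways. It first points to outside criteria: "Both MI and ST are to be determined by the Academic Research Consortium (ARC) classification criteria", and "MI to be classified into various types and include the 99th percentile upper reference limit (URL) decision limits for biomarkers employed". It then gives its own bullets in multiples of ULN. The Q-wave bullet looks back to baseline, since the Q-waves must be "not present on the subject's ECG before allocation". The other bullet reads "Non-Q-Wave MI: Elevation of post-procedure CK-MB levels to >3.0 times ULN without new Q-waves" and names no earlier value. The peri-operative rule for bypass surgery (total CK-MB above 5 times ULN, or new Q-waves) names no earlier CK-MB either.

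Protocol 5.3.5 sets three post-procedure CK-MB draws, at once, at 6-12 hours and at 18-24 hours: "The first draw should be performed immediately after the procedure".

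Protocol 6.4 has all clinical endpoints "adjudicated by an independent clinical events committee using definitions consistent with the investigational plan", and adds: "The CEC will develop a prospective CEC charter before any study data is adjudicated".

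The SAP lists MI in section 5.2.2, within MACE and under "Individual components of the MACE composite end-point", and again in Table 9. It does not restate a definition.

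**The concern.** The two descriptions use different reference limits, a 99th percentile URL and a multiple of ULN, and nothing ranks them. The Q-wave bullet asks for a new finding, but the bullet beside it does not say that CK-MB must have risen from a pre-procedure value. A subject who arrives with CK-MB above 3 times ULN could still be above it at the immediate draw, with the level already falling. On a bare-threshold reading that subject has an in-hospital MI, and therefore a MACE. If it is classed as a target vessel MI, it is also a TLF.

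The entry rules do not rule this out on paper. Unstable angina is eligible, the exclusion needs a diagnosed acute MI within 72 hours, and no enzyme cut-off is listed although enzymes are drawn for eligibility (Protocol Table 1.0, footnote a). With 60 subjects, one disputed case shows in the reported rate.

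**Working it through.** The documents state no MI rate, so there is no figure to reproduce. The check asks when the wording changes a classification, and by how much.

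**Inputs.** N = 60 (Protocol Summary). Threshold 3.0 times ULN (Protocol 6.2.2). Three post-procedure draws (Protocol 5.3.5). All CK-MB values below are assumed for illustration.

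**Step 1: two readings of the bullet.** Let b be the pre-procedure CK-MB and m the highest of the three draws, both in multiples of ULN, with no new Q-waves.

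- Reading A (threshold only): MI if m > 3.0.
- Reading B (rise required): MI if m > 3.0 and m > b.

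| b | Draws | m | A | B |
|---|---|---|---|---|
| 4.0 | 3.8 / 3.2 / 2.4 | 3.8 | MI | not MI |
| 3.2 | 3.2 / 3.2 / 3.2 | 3.2 | MI | not MI |
| 4.0 | 2.9 / 2.5 / 2.0 | 2.9 | not MI | not MI |
| 2.0 | 2.0 / 2.0 / 2.0 | 2.0 | not MI | not MI |
| 0.8 | 1.0 / 3.2 / 2.6 | 3.2 | MI | MI |

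The readings differ only when 3.0 < m ≤ b. The baseline must already exceed 3.0, at least one later draw must still exceed 3.0, and no draw may exceed the baseline.

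**Step 2: can such a subject be enrolled?** Protocol Table 1.0, footnote a, has CK/CK-MB drawn within 24 hours before the procedure for eligibility. Protocol 4.3.1 excludes a diagnosed acute MI within 72 hours, the listed criterion that draw most plausibly serves. A CK-MB above 3 times ULN is the level the protocol itself treats as an MI afterwards, so this subject is among the likeliest to be screened out. Because no cut-off is written, the path is narrow but not closed. Protocol 5.3.2 requires CK-MB only when CK Total is above 1 times ULN. Subjects without a baseline CK-MB for that reason are those least likely to have had a high one. Only subjects who qualified on troponin alone plausibly lack a baseline that matters.

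**Step 3: size per subject.** 1/60 = 1.67 percentage points on MI, and on MACE if the subject has no other component event. Exact (Clopper-Pearson) 95% intervals:

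| Events | Rate | 95% interval |
|---|---|---|
| 0/60 | 0.0% | 0 to 5.96% |
| 1/60 | 1.67% | 0.04 to 8.94% |
| 2/60 | 3.33% | 0.41 to 11.53% |

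One reclassified subject moves the estimate by less than the uncertainty already present at 0/60.

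**Step 4: how likely is at least one?** Let q be the share of enrolled subjects for whom the readings differ. The documents give no value, so q is an assumption. P(at least one) = 1 − (1 − q)^60.

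| q | Expected count (60q) | P(at least one) |
|---|---|---|
| 0.5% | 0.3 | 26% |
| 1% | 0.6 | 45% |
| 2% | 1.2 | 70% |
| 5% | 3.0 | 95% |

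Nothing in the documents selects a row, and q = 0 is equally consistent with them.

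**Step 5: does the protocol impose Reading A?** No. The bullets stand directly below the sentences invoking ARC and the URL limits, so the section can be read as one scheme: criteria first, working thresholds after. Reading A needs the bullet taken apart from those sentences, and no text says to do so. Whether the cited criteria deal with a raised baseline cannot be judged from these documents.

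**The case for a change.** The best case for acting is that the text is ambiguous and clarifying it is cheap. Two adjudicators could defend opposite calls from the same page, and Protocol 6.4 binds the committee to a plan that contains both descriptions. The authors thought of baseline for Q-waves and not for enzymes. SAP Table 3 has NSTEMI as a level of baseline angina status, so recent infarction may have been foreseen. SAP Tables 3 and 4 summarise CK-MB before the procedure and at each draw separately, so a reader could not tell carry-over from a new rise. A few sentences would cost no subjects, visits or assays.

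Part of this stands: precedence is unwritten, and neither the non-Q-wave bullet nor the bypass-surgery CK-MB rule names a comparator. The rest is weaker.

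- The NSTEMI row gives neither timing nor enzyme level, and an infarct older than 72 hours is eligible.
- The tables are summary shells. Adjudication works from each subject's own values, so they need not separate the two cases.
- The SAP need not repeat a definition that the protocol gives and the committee applies.
- The bullet speaks of post-procedure levels in the plural, which naturally means any of the three draws.
- Requiring a rise would itself need a stated size and a fallback for subjects without a baseline CK-MB. Those are adjudication details suited to the charter.

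**Conclusion.** The concern describes the wording correctly, but it does not call for a change to the plan. What is missing is an order of precedence and a rule for raised baselines. The protocol already gives an independent committee the task of setting its working definitions before any data are adjudicated, and experienced adjudicators would be expected to compare a post-procedure enzyme with the value before it. The charter is not among the documents, so this rests on its being written when Protocol 6.4 says and on its covering the point.

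The consequence is small. Each affected subject is worth 1.67 points, the number affected is unknown and may be zero, and the baseline gap can only add MIs, so it cannot make the device look safer. The effect of choosing the ARC/URL text over the ULN bullets cannot be sized from the documents, in amount or direction. Only MI, MACE and TLF are touched. All three are descriptive secondary endpoints, the study has no hypothesis or success threshold, and device procedural success does not use MI. The documents do not show that any subject would be misclassified.
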